3. STUDY DESIGN

This is a parallel groups interventional study consisting of 4 main sections: 1. Screening for OSA and enrollment of moderate to severe OSA in AA and other Veterans-, 2. Pre-treatment measurement of outcomes (ABP, CABP, SNA, oxidative stress, TTE/STE) and postulated moderators (PVT lapses/ESS and genetic ancestry), 3. Institution of laboratory titrated AUTOPAP treatment with adherence optimization, and 4. Assessment of AUTOPAP treatment effects after 3 months on outcomes and EDS measures, namely PVT and ESS.

Figure. Research Protocol Timeline

Key: ABP = 24-hour ambulatory blood pressure, CABP = Central aortic blood pressure, APAP = Auto-adjusting positive airway pressure; STE = Speckle-tracking echocardiography; PM = portable monitoring

Potential study participants will be identified from sleep, tele-sleep, and pulmonary specialty clinics at JBVAMC (second floor Ogden Pavilion). Additionally, we will post study information flyers in Primary Care clinics (first floor Ogden Pavilion). All study related patient visits will be at JBVAMC. All study related patient visits during normal business/clinic hours will be in (rooms 2295, 2292, and 2291, Taylor Pavilion, JBVAMC). The overnight visits for testing (Visit 2) will be in Hospital, Damen Pavilion, 9 West (rooms Room 9508, 9511, 9514, 9515, and 9516). Visit 3 (polysomnography) will be at Hines VA hospital, Building 200, Room # 1421, [name].

Initial Screening Visit #1: All eligible patients identified from the clinics noted above will be provided with the study information sheet by the PI/Study coordinator. Each patient that verbally assents will be provided with oral and written information (informed consent form) describing the study and will have all questions answered. Patients will be specifically consented for blood draw for AIMS measurement, tissue banking, and echocardiography. Patients who want time to decide regarding participation in this study will contact the research coordinator by telephone. The potential participants will be screened with the use of a telephone screening script. *Patients will be able to participate in the primary study without participating in these measures (venous blood draw and echocardiography).* Consenting patients will undergo preliminary eligibility assessments, including Berlin Sleep Questionnaire (BSQ), Epworth

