Sleepiness Score (ESS) questionnaire, Functional Outcomes of Sleep Questionnaire (FOSQ), complete medical history and physical examination, and CABP measurements. Enrollment of patients who have severely elevated blood pressure (>200/120 mm Hg) will be deferred and they will be referred to their primary care provider/urgent care as clinically appropriate.

All antihypertensive medications will be recorded (number, dose, and refill information) for each patient at baseline and at the end of the study (final visit). This information will be confirmed with the JBVAMC/or outside pharmacy for accuracy. Patients will be encouraged to follow up with primary physician per usual schedule and to avoid taking over-the-counter medications that may affect blood pressure (e.g., some cold medications) for 24 hours before and during the ABP monitoring.

All eligible patients will perform a 10-minute psychomotor vigilance task (PVT). Specifically, consenting patients will have venous blood sampling (35 mL) for processing (DNA, RNA, serum, and plasma) and storage at UI Biorepository as well as an echocardiography scheduled at JBVAMC. A urine pregnancy test will be done for women of childbearing potential. All enrolled patients will initiate 7-day actigraphy with concurrent sleep logs (to estimate average nightly sleep duration), 24-hour urine collection, and 24-hour ABP recordings at completion of visit 1 and will be scheduled for an overnight portable monitoring (PM) test at Jesse Brown VAMC (Visit 2) or at home. If the PM test fails to record data due to technical or application errors, the patients may be asked to repeat this test once. We will schedule an echocardiography test at JBVAMC for consenting patients (to be completed before visit 4).

Each measure to be performed is briefly described below. All are validated and commonly used in clinical practice and research:

- i. **PVT:** A 10-minute PVT192 test with a hand-held device for sustained attention will be conducted (Ambulatory Monitoring, Inc., Ardsley, NY), with a preceding 1-minute practice exercise. Participants will be using the hand held device and respond to the stimuli presented on the screen at random intervals by pressing a button. The PVT indicator of EDS will be frequency of lapses (instances where the patient fails to respond to the stimulus in a timely manner; Reaction Time, RT > 500 milliseconds).

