- ii. **ESS** is a self-administered questionnaire used to estimate sleepiness for eight different real-life situations. A score of ≥ 11 is indicative of EDS, while 0-10 is defined as normal.
- iii. **FOSQ10:** is a 10-item self-administered questionnaire to assess disease specific quality of life.
- iv. **Actigraphy** will measure and account for daily sleep duration objectively with 7-day recordings (Actiwatch 2⁰, MiniMitter, Philips Respironics, Andover, MA) in conjunction with a *sleep log*, a subjective daily log of sleep-wake schedule used for final scoring of actigraphy. This is important as sleep duration will affect daytime sleepiness assessments.

- v. **CABP** will be assessed using a brachial (upper arm) cuff-based FDA approved system; SphygomoCor XCEL (Atcor medical, Australia). This will be measured in a seated position after 5 minutes of rest at visits 1 and 5.
- vi. **ABP** will be recorded with the 90217 Ultralite ambulatory blood pressure monitor (Spacelabs, Issaquah, WA). Blood pressure measurements will be taken every 20 minutes in the day and every 30 minutes at night (9 PM to 6 AM, to minimize sleep disruption) for a 24-hour period. Recordings will be considered valid when at least 70% of expected measurements are available. Patients will be asked to repeat the ABP for failed recordings.
- vii. **24-hour Urine collection:** Patients will provide urine samples collected over 24 hours as two samples (after first void in the morning to 10 PM and from 10 PM to first void the morning). The patients will be provided appropriate urine collection system and overnight samples will be collected on ice and stored at the JBVAMC room 7200, Taylor Pavillion for isoprostanes to be performed. The overnight urine samples to be stored at JBVAMC will be labeled with unique study ID number and sample type only. 24-hour urinary excretion of catecholamines (SNA) will be measured from the pooled sample and this will be performed outside JBVAMC laboratory per standard clinical procedure.

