Tissue banking: blood processing for DNA, RNA, serum and plasma isolation and storage will be performed at UI Biorepository, under the supervision of [name], [name] and [name] (Clinical Science Building North, [name]). The blood samples to be carried outside JBVAMC will be labeled with unique study ID number only. Only the processing of blood will be done outside JBVAMC and the blood draw procedure will only be done at JBVAMC. The processing for JBVAMC is done at the Madison/Milwaukee VA lab. To avoid delays loss of sample or sample integrity, we want to hand-deliver the samples without individual identifiers to UIC for prompt processing.

- viii. **Echocardiogram** data will include myocardial mechanical data obtained by clinical software that is used in the clinical workstation in the JBVAMC echocardiography laboratory. This software is called Velocity Vector Imaging (VVI; Siemens Medical Solutions USA, Inc., Mountain View, CA). [name], JBVAMC cardiologist and collaborator will provide interpretation of these data.

Visit #2: Patients performing home PM will be instructed to begin ABP monitoring and urine sample collection the morning prior to the scheduled visit 2. Visit 2 will be in the morning and PM device, actigraphy, sleep log, urine sample, and ABP monitor will be collected and processed/downloaded. Patients performing PM test at JBVA will be instructed to begin ABP monitoring and urine collection the morning of scheduled visit 2. Patients will arrive for the overnight PM at JBVAMC. Actigraphy, sleep log, urine sample, and ABP monitor will be collected and processed/downloaded in the morning after completion of the PM test. PM tests will be performed using ALICE PDX (Phillips Respironics) or WatchPAT200 (Itamar Medical). PI has experience with both these devices that are available to us, are validated, used routinely in

clinical practice, and provide similar information with respect to screening for OSA. All patients with apnea hypopnea index (AHI) ≥ 15 /hour on the PM test will be invited to continue. This additional screening step with PM testing will reduce screen failure rates with PSG, which is more costly. We propose to allow both home PM and PM at JBVAMC in order to minimize scheduling conflicts between clinical and research tests scheduled.

Previously scheduled Visit 3 will be eliminated to reduce participant burden and improve recruitment to meet target sample of 220 over the next two years.

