Visit #3: Patients will return to the clinic for AUTOPAP treatment set-up and education by trained study coordinator. Patients and their bed partner will receive a one-on-one standardized education session describing the method of applying the device and individualized mask fitting will be performed; (4) patients will be called twice weekly in the first two weeks and once weekly thereafter to troubleshoot barriers to AUTOPAP use and encourage daily treatment application including during daytime naps.

Visit #4: Patients will return to clinic for repeat PVT, FOSQ, ESS, CABP measurements and to initiate 24-hour ABP and urine collection. Patients will also be scheduled for repeat echocardiography test in the following 3 months, if they had a pre-treatment echocardiography (to assess AUTOPAP treatment effects). No caffeine will be permitted during visits 1 and 5 to minimize interference with EDS assessments. Patients will also do venous blood sampling (35 mL) for processing (DNA, RNA, serum, and plasma) and storage at UI Biorepository

Final Visit # 5: Patients will return to clinic in the morning after initiating 24-hour ABP and urine collection, which will be collected and processed/downloaded. AUTOPAP devices contain a software system that records the duration of AUTOPAP use each day. These data will be accessed and recorded as final measure of AUTOPAP treatment adherence.

Patients will be given instructions regarding follow-up care for OSA with sleep medicine or primary care provider.

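### Follow-up ambulatory BP and urine start in clinic and are handed in the next morning, with no clock time or minimum duration, so they can lose daytime hours relative to baseline

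*Combined protocol and SAP*

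**What the plan says.** **Follow-up.** Section 3, Visit #4: "Patients will return to clinic for repeat PVT, FOSQ, ESS, CABP measurements and to initiate 24-hour ABP and urine collection". Visit #5: "Patients will return to clinic in the morning after initiating 24-hour ABP and urine collection, which will be collected and processed/downloaded". The synopsis says the same. Neither gives a time of day. Section 3 ties daytime visits only to working hours ("All study related patient visits during normal business/clinic hours will be in" named rooms).

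**Baseline, three accounts.**
- Section 3, Visit #2: "Patients performing home PM will be instructed to begin ABP monitoring and urine sample collection the morning prior to the scheduled visit 2". Patients tested in hospital "will be instructed to begin ABP monitoring and urine collection the morning of scheduled visit 2" and hand in the morning after the test. Both routes give about 24 h.
- Section 3, Visit #1, and the synopsis: enrolled patients begin "24-hour urine collection, and 24-hour ABP recordings at completion of visit 1", which is a clinic start.
- Appendix I: on a six-visit numbering, ABP and urine are initiated at Visits 2 and 5 and collected at Visits 3 and 6, the same pattern at both time points.

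**Measurement rules.** Section 3, item vi, samples every 20 minutes by day and every 30 minutes from 9 PM to 6 AM. It adds: "Recordings will be considered valid when at least 70% of expected measurements are available". Item vii defines the two urine samples as "after first void in the morning to 10 PM and from 10 PM to first void the morning". Appendix II expresses catecholamines per mole of creatinine.

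**The concern.** The primary outcome is change in average 24-hour systolic and diastolic BP (section 8, table). A patient whose monitor is fitted in the early afternoon and returned at 9 AM has a full night but a shortened day. Night pressure is usually lower, so the mean drops with no true change. If baseline was a full morning-to-morning recording, that drop is read as response to treatment. The within-group tests in section 9.4.2 have no untreated arm against which to detect it.

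Urine has a related problem. A patient who comes to clinic has normally already passed the first morning void, which item vii uses as the starting point. A collection begun at Visit 4 then omits everything between that void and the visit, even with a morning appointment.

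**Working it through.** The plan states no actual length for the follow-up recording beyond calling it 24-hour, so the check starts from the reading count that item vi implies. The sample size (99 per group, 220 enrolled) does not enter.

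**Expected readings (item vi).** Day, 6 AM to 9 PM: 15 h x 3 = 45. Night, 9 PM to 6 AM: 9 h x 2 = 18. Total 63; night share 18/63 = 28.6%. The 70% threshold is 0.70 x 63 = 44.1, so at least 45 readings are needed, taking the expected number as the full 24-hour count.

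**Effect of L lost daytime hours.** Readings N = 63 - 3L. Night share = 18/N. With day-night difference D and a simple mean of readings, spurious fall = D x (18/N - 18/63). Assumptions not in the documents: D = 10-20 mmHg, a 9 AM return, and the start times shown.

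| Start | L | N | % of 63 | Night share | Fall, mmHg | Failed readings tolerated |
|---|---|---|---|---|---|---|
| 9 AM | 0 | 63 | 100 | 28.6% | 0 | 18 |
| 11 AM | 2 | 57 | 90.5 | 31.6% | 0.3-0.6 | 12 |
| 1 PM | 4 | 51 | 81.0 | 35.3% | 0.7-1.3 | 6 |
| 3 PM | 6 | 45 | 71.4 | 40.0% | 1.1-2.3 | 0 |
| 4 PM | 7 | 42 | 66.7 | not valid, repeat | - | - |

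Example, L = 6: 18/45 - 18/63 = 0.400 - 0.286 = 0.114; times 10 and 20 gives 1.1 and 2.3.

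**Between groups.** An equal shift cancels in the two-sample t-test on change. If both groups lost 6 h and had day-night differences of 10 and 15 mmHg (assumed), the residual is 0.114 x 5 = about 0.6 mmHg.

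**Urine, per creatinine.** Assume constant creatinine excretion, a day:night catecholamine excretion-rate ratio r of 1.25-2.0 (not in the documents) and the same 15 h/9 h split. The full-collection ratio is proportional to (15r + 9)/24 and the truncated one to ((15 - L)r + 9)/(24 - L).
- L = 2: fall 0.7% (r = 1.25) to 2.1% (r = 2.0)
- L = 4: 1.6% to 4.6%
- L = 6: 2.7% to 7.7%; for r = 2.0, 27/18 = 1.500 against 39/24 = 1.625

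Total excretion would fall far more (27-31% for L = 6), but that is not the scale in Appendix II. Overnight 8-isoprostane is unaffected, because its sample starts at 10 PM.

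**Is baseline exposed in the same way?**
- Visit 2 text: morning start, next-morning hand-in; not exposed beyond ordinary variation in clock time.
- Start at completion of Visit 1: the monitor is handed in at Visit 2 together with a 7-day actigraphy recording begun at the same visit, so ABP has time to complete 24 h. Urine begun in clinic would lose the hours since the first void, as at follow-up.
- Appendix I: the same visit-to-visit pattern at both times, so no asymmetry can be read from it.

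**The case against.** A reader might infer that follow-up recordings do fall short of 24 h while baseline recordings do not, and that the trial will therefore show a false fall in BP and catecholamines. The documents do not support that. No clock times are given. A Visit 4 start at 9 AM with return at 9 AM satisfies the text and yields all 63 readings. The full contrast with baseline rests on the Visit 2 instructions. Appendix I shows no asymmetry, and a clinic start at Visit 1 would truncate baseline urine in the same way.

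The 70% rule also gives partial protection. With 6 h lost, one failed reading leaves 44 of 63 (69.8%) and triggers a repeat. The 1.1-2.3 mmHg figure is therefore a ceiling for a patient with a mid-afternoon start and no failed reading, not an expected study-level bias. Nothing in the documents suggests that appointment times or day-night differences vary by group, so the effect on the main comparison is likely small.

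All of this stands and limits the claim. It does not remove the gap: the text permits an afternoon start with a morning return, sets no minimum duration or daytime count, and starts follow-up urine at a point that ordinarily does not meet the item vii definition.

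**Conclusion.** The point holds as a risk that the text permits, not as a demonstrated shortfall. Follow-up ABP is short whenever Visit 4 starts later in the day than the Visit 5 return. The loss is then entirely daytime, the direction is a spurious fall, and the validity rule can miss losses of up to 6 h. The sizes rest on a simple mean of readings, the assumed day-night difference and illustrative clock times. The bias falls mainly on the uncontrolled within-group change. It reaches the comparison of African American with other veterans only if visit times or day-night differences vary by group. The urine start normally conflicts with item vii, with a probably small effect on the per-creatinine outcome. The correction is worth making because it is cheap and the affected variable is the primary outcome.

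**What to change.** 1. Reconcile the synopsis, section 3 (Visits 1, 2, 4 and 5) and Appendix I so that baseline and follow-up share one start rule: urine after the first morning void and ABP in the morning, as the Visit 2 text already has it. Hand-in should be at least 24 h later. One way is to dispense monitor and containers at Visit 4, start both the next morning, and hold Visit 5 the morning after that. Fixing Visit 4 in the morning and Visit 5 no earlier in the day would close the ABP gap but not the urine gap.
2. Record start and stop clock times at both time points, and add a minimum duration or a minimum number of daytime readings to the 70% rule.
3. For patients already measured, compute ABP change over the clock hours present in both recordings, or weight the day and night means by fixed hours (15 and 9). Weighting by the hours actually recorded does not help: with 6 h lost, the day weight falls from 15/24 to 9/18, a shift of 0.125 x 10-20 = 1.25-2.5 mmHg.

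Cost: an amendment to wording, Visit 5 one day later, and cuff fitting at home, which the Visit 2 instruction already implies at baseline. No visit or test is added. The common-hours analysis describes those hours rather than the full 24, which should be stated when it is reported.

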4.2 Exclusion Criteria

A patient will be excluded from this study if he or she meets any of the following criteria:

1. Past/current treatment of OSA or other primary sleep disorders;
2. Active uncontrolled medical or psychiatric conditions (for e.g. heart failure, chronic lung disease, depression etc.);
3. Shift work in past 1 month;
4. Current Illegal drug use, daily alcohol use, or a positive urine drug screening test in the preceding 6 months;
5. Pregnancy (every woman of childbearing age group will have a urine pregnancy test on visit 1);
6. Use of dietary supplements which in the judgment of the PI may impact sleep or breathing behaviors;
7. Average daily caffeine consumption > 500 mg/day (~5 cups of coffee);

5. CONCOMITANT MEDICATIONS (ANTIHYPERTENSIVES)

Antihypertensive medications will be recorded (number, dose, and refill information) for each patient at baseline and at every visit thereafter. This information will be confirmed with the patient's pharmacy for accuracy at visit 1 and 6. Patients will be encouraged to follow up with primary physician per usual schedule and to avoid taking over-the-counter medications that may affect blood pressure (e.g., some cold medications) for 24 hours before and during the ABP

monitoring. Adherence to medications for hypertension will be defined by the Medication Possession Ratio (MPR; performed by examining pill vials at visits 1, 2, 6, and 8). MPR calculation results in values of 0-1.0 (1.0 = perfect adherence). An MPR will be calculated for each antihypertensive drug, and the mean MPR for all antihypertensive drugs will be used as a measure of adherence to medication treatment. To adjust for changes in antihypertensive regimen or dosage of drugs that may occur during the study, we will use the Defined Daily Dose (DDD). The World Health Organization; WHO DDD methodology (<http://www.whooc.no/atcddd/>) allows for comparison of BP medications across antihypertensive regimens using “the average maintenance dose per day for a drug.” Because no class of antihypertensive drugs is known to be superior in OSA, this approach will allow examination of the potential blood pressure lowering effect of AUTOPAP across the inter-individual and intra-individual variations in antihypertensive medication regimens.

6. STUDY DISCONTINUATION

The PI may recommend discontinuation of participation of individual patients. Reasons for early patient discontinuation may include: inability to tolerate AUTOPAP, development of severe blood pressure elevation (> 200/120 mm hg) or other unstable medical conditions during study participation, request to discontinue the trial from the patient or a regulatory authority, or protocol violations.

7. ADVERSE EVENTS

7.1 Definition- An AE is any adverse change from the patient’s baseline condition, including any clinically significant signs and symptoms that occurs during the course of the study after the patient is enrolled, whether the AE is considered expected/unexpected and related to the treatment or not.

7.2 Adverse Event Reporting

7.2.1 Routine Reporting of Adverse Events

All AEs encountered during the clinical study that are considered study related, will be recorded in the source documents. All new events, as well as those that worsen in intensity or frequency relative to baseline, which occur after enrollment through the period of protocol-specified follow-up (visit 6) will be recorded.

The information to be recorded for each AE includes:

1. Medical diagnosis of the event in standard medical terminology (if a medical diagnosis cannot be determined, a description of each sign or symptom characterizing the event should be recorded);
2. Date of onset of any new AE or the date of worsening of a previously observed AE;

3. Date of resolution of the event;
4. Severity of the event;
5. Assessment of the attributability of the event to the study protocol;
6. Whether the event is serious;
7. Whether the event is expected;
8. Description of action taken in treating the event (include medications or therapies administered, whether hospitalization was required, diagnostic procedures performed, and whether the patient was discontinued from the study);
9. Description of outcome: resolved or complete return to baseline, resolving, unknown/lost to follow-up, AE persisting or resolved with sequelae.

All AEs will be followed until resolution or stabilization of the event. This may require additional clinical assessments. The follow-up results will be recorded in the patient's source documentation.

